**Secondary Outcome (Patient Engagement):** We will measure patient engagement in treatment at assessment 1 as well as at assessments 2, 3 and 4. Patient engagement is a complex phenomenon to measure. The term 'patient engagement' encompasses various aspects of care related to a patient's motivation and intent to be an active participant in addressing their healthcare needs. To date, there is no agreed-upon measure in the literature that incorporates all aspects of the experience of 'patient engagement'. In the field of mental health, there is some notion that 'patient engagement' should mean that a patient experiences collaborative care, feels supported during their treatment, and adopts 'good practices' or behaviors that support their overall well-being. Therefore, only assessing whether a patient attended a mental health appointment may not adequately reflect treatment engagement. There is also evidence that symptom severity can preclude patients from engaging in care. Pfeiffer *et al.* found that, despite improvements in timely outpatient follow-up after VA psychiatric hospitalization, there were no significant changes in readmission or antidepressant treatment. In fact, Bernet *et al.* found that appointment intensity was higher in Veterans who reattempted suicide after discharge versus those who did not reattempt. Furthermore, in reviewing our data thus far from our trial on Ground East, we have identified that our current measures of engagement may not be adequately covering a key component of patient engagement as it relates to suicide including self-efficacy around managing suicide risk. This is a key concept that is part of the VA BIC intervention. Thus, we conceptualize that engagement includes patient activation, continuity of care, and self-efficacy.

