## **Statistical Considerations**

**Statistical Analyses:** To maintain blinding, the statistician who is otherwise not directly involved in the study will conduct the analysis based on the intention-to-treat principle. Below, we have outlined the specific analysis plan for assessing each of the three aims of interest of this study. As part of the analyses of the three aims, we plan to account for potential confounding. We will assess for statistically significant differences in baseline study characteristics, including age, sex, race, history of suicide attempts, mental health diagnosis, marital status, employment, recent life stressors, service history, High Risk for Suicide List status, and Suicide Prevention Pathway status between study arms using *t*-tests for continuous measures and chi-squared tests

for dichotomous variables. We will report these results using 95% confidence intervals (CI) and *P*-values. We will define statistical significance as a *P*-value < 0.05. If we identify any variables for which there are significant differences across study arms, we will control for these confounders in the analysis of the aims.

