We will calculate 95% CI and *P*-values and will define a *P*-value of < 0.05 to be statistically significant. We will use the maximum likelihood ratio to account for any missing data.

**Specific Aim 2:** The secondary aim of our study is to determine the mechanism by which PEACE exerts its anti-suicidal effect on patients after psychiatric hospital discharge. Based on available evidence, we hypothesize that the intervention plus standard psychiatric hospital discharge care exerts an anti-suicidal effect on patients after psychiatric hospitalization by improving social connectedness and engagement in care after discharge. We will assess this aim by performing the following analyses: First, we will perform an analysis to demonstrate whether there are greater improvements in social connectedness and engagement in care over time in patients assigned to the intervention versus control condition at one, three, and six months after discharge. For continuous variables measuring patient engagement, we will generate descriptive summary statistics (e.g., means and standard errors, medians) and graphical displays for each measure at baseline (assessment 1) and at assessments 2, 3, and 4. Second, using structural equation modeling, we will calculate mean differences in scores for each of our continuous measures at the one-, three-, and six-month assessment periods, as well as the associated 95% confidence intervals and *P*-values. For the categorical measure of patient engagement, we will use chi-squared tests to compare the proportion of patients adhering to their discharge plan between the two study arms at one-month after discharge. Third, we will assess whether social connectedness and patient engagement mediate the effect of the intervention on suicidal ideation, as measured by total BSS scores. In order to conduct this analysis, we will use structural equation modeling. We will use the maximum likelihood to account for any missing data. We will calculate the associated 95% CIs and *P*-values and will define a *P*-value of 0.05 to be statistically significant.

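### The covariate rule for Aim 2's mediation analysis selects on arm differences, so it will rarely remove mediator-outcome confounding

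*Combined protocol and SAP*

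**What the plan says.** All references are to the combined protocol and SAP.

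- **Statistical Considerations, Statistical Analyses.** One confounding rule serves every aim: "As part of the analyses of the three aims, we plan to account for potential confounding". Baseline characteristics are tested between arms, and where there are "significant differences across study arms, we will control for these confounders in the analysis of the aims". The threshold is given as "We will define statistical significance as a *P*-value < 0.05".
- **Variables screened.** Eleven are named: "age, sex, race, history of suicide attempts, mental health diagnosis, marital status, employment, recent life stressors, service history", plus High Risk for Suicide List status and Suicide Prevention Pathway status. Baseline BSS, hopelessness (BHS), INQ-15, MSPSS and SRCS are not named, although Table 2 collects all five at baseline.
- **Specific Aim 2.** The purpose is a mechanism: "The secondary aim of our study is to determine the mechanism by which PEACE exerts its anti-suicidal effect on patients". The third step is that "we will assess whether social connectedness and patient engagement mediate the effect of the intervention on suicidal ideation", with total BSS as outcome, structural equation modelling as method and maximum likelihood for missing data. No covariates for the mediator or outcome equation and no sensitivity analysis for unmeasured confounding are given.
- **Outcome Measures, Secondary Outcome (Patient Engagement).** "There is also evidence that symptom severity can preclude patients from engaging in care". The same paragraph cites a study in which Veterans who reattempted suicide had more intensive appointment use than those who did not.

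**The concern.** Randomisation protects two comparisons in a mediation model: arm to mediator and arm to BSS. It does not protect the path from mediator to BSS, because nobody is randomised to a level of connectedness or engagement. The variables that matter for that path are those that predict both mediator and BSS. Whether they differ between arms says nothing about this. With well-balanced arms the rule adjusts for nothing, and the mediator-to-BSS path is left as confounded as it was.

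The protocol itself points to severity as such a variable. If severity lowers engagement or connectedness and also raises later BSS, part of the mediator-BSS association is severity. Once PEACE shifts the mediator, that association is multiplied into an indirect effect. What is at stake is the mechanism claim of Aim 2, which is meant to inform a later proposal. The Aim 1 comparison of arms is not affected.

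**Working it through.** **Inputs from the plan.** Sample Size: d = 0.5, 80% power, alpha 0.05, four time points, correlation of repeated measures 0.5, 40 per arm. The plan gives no figure for the mediation analysis. Its sample size reproduces with the usual formula for an average over time:

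n per arm = 2(1.960 + 0.842)² × [1 + 3 × 0.5] / (4 × 0.5²) = 39.2, so 40, as stated.

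The 0.5 correlation therefore belongs to repeated BSS measurements. It lends some support to a severity-to-later-BSS correlation of 0.5. It says nothing about severity and the mediator.

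**Assumed inputs (not in the documents).** Baseline severity U, standardised; correlation g_m with the mediator and g_y with BSS within arm; PEACE shifts the mediator by a SD; the mediator has no effect on BSS (b = 0).

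**Step 1: chance of passing the screen.** Under randomisation U differs between arms at P < 0.05 in about 5% of trials, however strongly it links mediator and BSS.

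**Step 2: bias.** With U left out, the mediator coefficient in the BSS equation is b + g_m × g_y, so the apparent indirect effect is a × (b + g_m × g_y). With a = 0.5, g_m = g_y = 0.5 and b = 0, this is 0.5 × 0.25 = 0.125 SD. The rule leaves about 95% of it: 0.95 × 0.125 = 0.119. Simulation gives 0.117 to 0.119 under the rule, and about zero with U always included.

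**Step 3: false claims.** Simulated trials, 40 per arm, mediation declared when both paths have P < 0.05. Severity-to-BSS correlation 0.5, mediator shift 0.5 SD, 20,000 trials per row:

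| Severity-to-mediator correlation | Plan's rule | U always in model |
|---|---|---|
| 0.1 | 4% | 3% |
| 0.2 | 8% | 3% |
| 0.3 | 15% | 3% |
| 0.4 | 24% | 3% |
| 0.5 | 35% | 4% |

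Other runs of the last row under the rule gave 33% and 37%.

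**Step 4: dependence on the mediator shift.** With correlation 0.5 on both legs, the rule gives about 35% at a 0.5 SD shift, 13% to 15% at 0.3 SD, 7% to 8% at 0.2 SD and 2% to 3% at no shift. At 0.8 SD it gives 55%.

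**Step 5: the opposite direction.** Take the number of mental health visits, the plan's intensity-of-care measure. If sicker patients attend more, g_m and g_y are both positive, while the hypothesised b is negative. With g_m × g_y = +0.25, a true b of -0.25 is estimated as -0.25 + 0.25 = 0, and real mediation disappears.

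**The case against.** **The plan leaves room.** The list of screened variables is introduced as examples, it already holds attempt history and diagnosis, and the structural equation model is unspecified, so an analyst could add baseline BSS and baseline mediator values. This stands in part. The text does not rule such terms out, but it does not commit to them, and the one rule it states would admit them only on an arm difference. A reader might infer that the rule can never remove the confounding. That is too strong: a confounder that happens to be imbalanced, about 1 in 20, would be adjusted for.

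**The percentages are not the plan's.** A reader might take the figure of about 35% as resting on the plan's own correlation. It does not. The documents give no severity-to-mediator correlation, and their d of 0.5 is for BSS, not for a mediator. This stands in full.

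**Severity alone is not enough.** A reader might infer that sicker patients scoring worse on both measures suffices for a false finding. It does not: PEACE must also move the mediator. In the nine-patient pilot (Table 1) both INQ-15 scales improved, but no social support scale changed significantly.

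**The direction is not fixed.** The sentence on severity concerns engagement, not connectedness, and the report on appointment intensity points the other way. This stands: the bias can mask mediation as well as create it.

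**Status.** Mediation is the third step of a secondary aim. True, though Aim 2 is worded as determining the mechanism and sets a 0.05 threshold.

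**Conclusion.** The concern holds on principle. The plan applies an arm-difference rule to a model whose vulnerable path is not randomised, so the rule picks covariates on the wrong criterion and will rarely (about 5% of the time for a given variable) remove mediator-outcome confounding. If PEACE moves the mediator, shared severity can produce a false indirect effect; for visit intensity it can conceal a true one.

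The size is illustrative only. It rests on an assumed single measured confounder, an assumed mediator shift and assumed correlations. The false-mediation rate runs from near nominal, when the severity-to-mediator link or the mediator shift is weak, to about a third at correlation 0.5 on both legs with a 0.5 SD shift. The 3% to 4% after adjustment is a best case, because in the simulation the only confounder is the one adjusted for. Confidence is high for the principle and not for any one percentage. The documents do not support reading this as a flaw in the sample size or in the comparison of arms.

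**What to change.** In Specific Aim 2, for the mediation models, replace the arm-difference rule with covariates fixed in advance and entered in both the mediator and the outcome equations whatever the arm balance:

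- baseline BSS;
- the mediator's own baseline value where one exists (INQ-15, MSPSS and SRCS have one);
- baseline BHS;
- prior suicide attempts.

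Add a sensitivity analysis that reports how large a residual mediator-outcome correlation would bring the indirect effect to zero. This is needed because baseline adjustment does not deal with unmeasured or post-baseline confounding. Word positive results as consistent with mediation, not as having established the mechanism.

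The cost is a change of SAP wording, a few degrees of freedom and more cautious claims. Every covariate is already collected at assessment 1, so visits and sample size are unchanged.

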AES = App Engagement Scale; BHS = Beck Hopelessness Scale; BSS = Beck Scale for Suicidal Ideation; CSSR-S = Columbia Suicide Severity Rating Scale; INQ-15 = Interpersonal Needs Questionnaire-15; M = months; MINI = MINI International Neuropsychiatric Interview; MSPSS: Multidimensional Scale of Perceived Social Support; N/A = Not applicable; SRCS: The Suicide-Related Coping Scale; \*Time is described in minutes

**Baseline Characteristics:** We will collect socio-demographic data from patient report and the electronic medical record such as age, sex, marital status and service history (e.g., branch, era, combat exposure). We will also collect diagnostic information using the MINI International Neuropsychiatric Interview (MINI), which has been validated against the Structured Clinical Interview for Diagnostic and Statistical Manual of Mental Disorders (DSM). The MINI is a short, structured diagnostic interview that, on average, takes about 15 minutes to administer. We will inquire about any history of suicide attempts using the validated Columbia Suicide Severity Rating-Scale (C-SSRS). The C-SSRS includes a 7-item subscale that assesses for actual and interrupted suicide attempts.

**Primary Outcome (Suicidal Ideation):** The primary outcome will be assessed using the Beck Scale for Suicidal Ideation (BSS). Patients will be asked about their current suicidal ideation (i.e., past week) at assessments 1 as well as at assessments 2, 3, and 4. The BSS is a self-reported questionnaire that assesses severity of suicidal ideation. The BSS measures attitudes, behaviors, and plans to die by suicide. Each item on the BSS is scored on a scale from 0 to 2 and the first 19 of the 21 items are used to calculate a total score ranging from 0 – 38. The BSS has high reliability and is a valid measure of suicidal ideation. There is also evidence that the BSS is measurement invariant across time. The BSS is widely used in clinical trials, is sensitive to clinical change, and unlike most other measures of suicidal ideation, higher scores on the BSS are associated with death by suicide. While there is no established BSS cutoff score to classify suicide risk as

high, low, or none, there is evidence that higher scores on the BSS correspond to more severe suicidal ideation. There is evidence that an improvement of five points or more on the total BSS scores may be clinically relevant.

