
suicide risk.

**Secondary Outcome (Suicide Attempts):** We will assess for non-fatal and fatal suicide attempts at one and three months after discharge using the C-SSRS. The C-SSRS is a valid and reliable scale that includes a seven-item subscale that asks patients to self-report on actual attempts, interrupted attempts, aborted attempts, and preparatory acts or behaviors. The scale asks the assessor to document the actual and potential lethality of these behaviors. The C-SSRS is widely used in the VA. The psychometrics of the C-SSRS in Veterans is unknown. We will also review suicide behavior reports (SBR) in the electronic medical record. SBRs are required in the VA and include information on suicide attempts, suicide deaths, and other types of suicidal behaviors including interrupted attempts.

[figure not shown]
**Secondary Outcome (App engagement):** Several measures have been selected to aid in a planned secondary analysis of the data to characterize the relationship between app engagement and outcomes in patients assigned to the intervention arm. Although mHealth is being used with increasing frequency to address various health behaviors, there is a dearth of evidence on effective methods to assess app engagement, though many approaches exist. Therefore, we will administer the App Engagement Scale (AES) at one-, three-, and six- months. Notably, the one- and three-month AES assessment will include the period during which the patient is receiving the PEACE intervention; however, the six-month assessment will measure whether the Veteran decided to continue to use the app on their own even after the intervention period ended and the intervention staff member was removed from the social network. The AES is adapted from the end-user version of the Mobile Application Rating Scale (uMARS). The AES has been studied in patients with mental health conditions, has been shown to have good internal reliability, and is strongly related to app engagement.

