**Specific Aim 3:** We plan to conduct an exploratory analysis on the number of suicide attempts (fatal and non-fatal) that occur after discharge in the intervention plus standard psychiatric hospitalization discharge care arm compared to standard psychiatric hospital discharge care, alone. While suicide deaths and suicide attempts are important clinical endpoints, this single-site trial will not be powered to detect a statistically significant effect between study arms. Furthermore, because we assume that few events will be observed in either arm, we plan to summarize our findings by providing basic descriptive statistics regarding the number of events in each arm at one-, three-, and six-month follow-ups. In the event that there are a sufficient number of suicide attempt events to perform statistical analysis, we will use a log-rank statistic to test for statistically significant differences in the proportion of suicide attempts between arms. We will use the Kaplan-Meier method to plot and compare survival curves for each arm. Specifically, we will calculate the time from the baseline assessment (assessment 1) to first suicide attempt after discharge for each study arm. Patients who are lost to follow-up or do not attempt suicide will be censored during the analysis. We will calculate hazard ratios using the Cox proportional hazards model. This approach will also enable us to adjust for baseline differences between study arms, if necessary. We plan on using these data to inform a future trial that is powered to detect an effect.

**Proposed Secondary Analysis:** Within the intervention group, we will conduct a secondary analysis of engagement with the mHealth app to assist further in the interpretation of our findings. Specifically, we are interested in learning about the degree to which patients assigned to PEACE interacted with app and whether differences in the degree of engagement with the app are associated with changes in social connectedness and suicidal ideation. First, we will generate descriptive summary statistics (e.g., means and standard errors, medians) and graphical displays for app engagement at one and three-month follow-up. Second, we will use generalized linear modeling to evaluate the relationship between app engagement and the primary outcome, suicidal ideation, and the secondary outcome, social connectedness.

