### Sample Size:

Based on a pilot RCT of the VA BIC Program in 19 patients discharged from the WRJ VAMC inpatient mental health unit (manuscript currently under review), we found that the intervention had an estimated effect size of 0.5 (Cohen's  $d_s$ ) on the BSS. We see the 0.5 as a medium sized effect and consistent with effects of other psychosocial interventions. We have reason to believe that this effect size may be even higher in our trial where we will be

enhancing the intervention with the addition of the mHealth app. We used these pilot data to re-calculate the required sample size for this proposed study. In doing so, we used a formula for

Table 3. Sample size estimates

Power	Alpha	$p$	n	Effect Size	Size of Effect	Intervention	Control	Intervention	Control
0.8	0.05	0.5	4	0.3	Small	109	109	120	120
0.8	0.05	0.5	4	0.5	Medium	40	40	46	46
0.8	0.05	0.5	4	0.6	Medium	27	27	30	30
0.8	0.05	0.5	4	0.8	Large	16	16	18	18

*p = correlation of repeated measures; n = 4 timepoints; N=number*

*\*Size of effect are based on criteria described in Laken D 2013.*

estimating sample sizes for longitudinal designs with repeated measures as proposed by Hedeker et al (1999). We assumed that the correlation of repeated measures ( $p$ ) was 0.5 based on findings from our pilot data. Furthermore, we assumed that there were four assessment points and that the data followed a normal distribution. We made this latter assumption because our pilot data followed a normal distribution according to the Shapiro-Wilk test for normalcy. We also are assuming that the data that we collect in this proposed trial will follow a normal distribution because the data will be drawn from the same population (and the same setting) as our pilot work. As shown in **Table 3**, based on the aforementioned calculations, a sample size of 80 (40 per arm) will achieve an 80% power to detect an effect size of 0.5 (Cohen's  $d$ ) or greater between arms across the study timepoints with a significance level of 5%. In our pilot study, there were no patients who dropped out, but

two patients had missing data at one or three-month follow-up. Conservatively, we assumed that in the proposed trial that there could be a drop out as high as 10%. This means that we will need to recruit for this proposed trial a sample size of **92** (46 per arm).

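### The within-PEACE app-engagement analysis names a plain generalized linear model and does not say how repeated visits or baseline values enter; if visits are pooled as independent rows, its standard errors would probably be too small

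*Combined protocol and SAP*

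**What the plan says.** The analysis is confined to one arm: "Within the intervention group, we will conduct a secondary analysis of engagement with the mHealth app". Its purpose is to learn "whether differences in the degree of engagement with the app are associated with changes in social connectedness and suicidal ideation". The model is given in one clause: "we will use generalized linear modeling to evaluate the relationship between app engagement and the primary outcome, suicidal ideation, and the secondary outcome, social connectedness". Nothing is said about a random effect, GEE, robust variance, visit term, baseline covariate or unit of analysis.

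The data behind it are longitudinal:

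- **Engagement.** In the Outcome Measures section, "we will administer the App Engagement Scale (AES) at one-, three-, and six- months". The same paragraph explains that the first two administrations fall within the intervention period. The six-month one captures voluntary use after the therapist has left the app's network.
- **Outcomes.** Table 2 schedules the BSS, INQ-15 and MSPSS at baseline and at one, three and six months.
- **Visits in the analysis paragraph.** The descriptive step covers only "graphical displays for app engagement at one and three-month follow-up". The modelling sentence names no visits.

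The Sample Size section does treat the trial as a repeated-measures design, and says that the correlation "was 0.5 based on findings from our pilot data".

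**The concern.** A generalized linear model in its ordinary form treats each row as independent. Each PEACE patient can supply two or three pairs of engagement and outcome values. The plan elsewhere assumes that repeated values on one patient correlate at 0.5, but this analysis does not carry that over. If the rows were pooled, patients who tend to be high or low on both variables would be counted several times, and intervals and P-values would be too favourable.

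The question about changes raises a second problem. The baseline value of the outcome does not appear in the model. Even a separate model at each visit, fitted to the outcome as written, would relate engagement to the level of ideation or connectedness and not to its change.

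This is the only planned analysis that relates app engagement to ideation or connectedness. The Aim 2 mediation model uses connectedness and patient engagement, and no arm receives VA BIC without the app. The result is therefore likely to be read when the next study is planned, even though it is secondary.

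**Working it through.** **Inputs**

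- Outcome correlation ρy = 0.5: Sample Size section, stated for the BSS calculation. Using it for the INQ-15 and MSPSS is an assumption.
- Patients: 46 recruited to PEACE, 40 evaluable (Sample Size section).
- Visits m: 2 (those summarised in the analysis paragraph) or 3 (those at which the AES is collected).
- Within-patient correlation of engagement ρx: not in the documents, so shown as a range.
- Nominal level: two-sided 5%, assumed. The paragraph on this analysis states no threshold.
- Exposure: the AES. The plan also mentions downloaded app-use data, for which no correlation is given either.

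**The plan's own figure.** Table 3 at effect size 0.5, with four time points and ρ = 0.5:

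n = 2(z₀.₉₇₅ + z₀.₈₀)² × [1 + (4 − 1) × 0.5] / (4 × 0.5²) = 39.24, so 40 per arm, as stated. Dropout of 10% gives 40/0.9 = 44.4, so 45 per arm against the stated 46, which is immaterial. The 0.5 therefore does enter the plan as a correlation between repeated measures.

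**Pooled rows, clustering ignored.** The true variance of the engagement slope exceeds the model's by the factor

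F = 1 + (m − 1) × ρx × ρy,

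and the actual rejection rate with no association is 2[1 − Φ(1.96/√F)].

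| Visits | ρx | F | Model SE as share of true SE | Rejection rate |
|---|---|---|---|---|
| 2 | 0 | 1.00 | 100% | 5.0% |
| 2 | 0.5 | 1.25 | 89% | 8.0% |
| 2 | 1 | 1.50 | 82% | 11.0% |
| 3 | 0 | 1.00 | 100% | 5.0% |
| 3 | 0.5 | 1.50 | 82% | 11.0% |
| 3 | 1 | 2.00 | 71% | 16.6% |

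A simulation with 46 patients, normal outcomes and 20,000 replicates agrees. It gives 8.0% and 10.9% for two visits, and 10.9% and 17.0% for three, at ρx = 0.5 and 1.

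**Sensitivity to ρy.** For ρy from 0.3 to 0.7, with ρx from 0.5 to 1, the rate runs from 6.8% to 13.3% with two visits and from 8.6% to 20.6% with three.

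**Cases without inflation**

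- One row per patient (a single visit, or one change score): m = 1, F = 1, rate 5.0%.
- Engagement uncorrelated within patients: ρx = 0, F = 1, rate 5.0%.
- Engagement varying only within patients: the pooled test is conservative, at about 0.7% in simulation.

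**Is a clustered standard error enough?** In the same simulations, an ordinary patient-clustered sandwich on two or three pooled visits with 40 to 46 patients rejected about 6% to 7% of the time. That is better, but a small-sample correction is still needed.

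**The case against.** The strongest reply is that the plan never says visits will be pooled. A change score per patient, or one model per visit, fits the wording and has valid standard errors. A visit-specific model can also address change, because the outcomes are all measured at baseline and the baseline value could be added. The protocol even gives a reason to keep visits apart, since six-month engagement means something different from engagement during the intervention. All of this stands. It makes the error-rate result conditional, and it argues against forcing a single pooled coefficient. It does not supply the missing baseline term or choose among the possible analyses, which could give different answers.

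Three stronger readings are tempting, and the documents do not support them:

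- *That the P-values and intervals are too favourable as a matter of fact.* That needs pooling, which is not stated, and engagement that is stable within patients, for which there is no figure.
- *That false positives more than double.* At two visits and an engagement correlation of 0.5 the rate is 8%. Only the three-visit case, or a very stable engagement score, reaches double. No 5% threshold is attached to this analysis.
- *That the plan would announce an app effect that does not exist.* It speaks of a relationship and of association. Engagement is not randomised, so correct standard errors would not make the result causal.

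It is also fair to say that the Aim 1 hurdle model names no patient-level term. That is a separate matter and does not settle this one.

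**Conclusion.** The concern holds in conditional form. The named model does not fit the structure of the data or the question. Pooled over visits, it would understate the error when engagement is fairly stable within patients. Fitted per visit to the outcome as written, it omits the baseline value that a question about change needs.

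Under pooling, the size is about 8% to 11% actual error at two visits and 11% to 17% at three, against a nominal 5%. This rests on an outcome correlation of 0.5 and an assumed engagement correlation of 0.5 to 1. With one row per patient, or no within-patient correlation in engagement, there is no inflation, and the direction can reverse.

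Severity is low. The analysis is secondary, confined to one arm and observational, and the randomised primary comparison does not depend on it. It is still worth correcting before analysis, because a better model is available at almost no cost.

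**What to change.** In Statistical Considerations, Proposed Secondary Analysis:

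1. Replace the model with a generalized linear mixed model with a random patient intercept, or a GEE clustered on patient with a small-sample variance correction.
2. Include visit as a factor and the baseline value of the outcome as a covariate.
3. State which visits are used.
4. If the six-month visit is included, keep its engagement association distinguishable from the one- and three-month association, for example with an engagement-by-visit term.
5. Report the result as an association, with its confidence interval, and not as an effect of the app.

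The cost is a few sentences of SAP text, with no new data, visits or staff. Compared with pooling and ignoring the clustering, intervals for a common engagement coefficient would be wider by about 12% at two visits (√1.25 = 1.12) and 22% at three (√1.5 = 1.22), with both correlations at 0.5. A separate six-month coefficient would be less precise than a common one.
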